This is a phase 3, 12-week, multicenter, randomized, double-blind, placebo-controlled, 3-arm, fixed-dose trial designed to assess the efficacy, safety, and tolerability of brexpiprazole (1 mg/day and 2 mg/day) in the treatment of subjects with agitation associated with dementia of the Alzheimer's type. The trial population will include male and female subjects between 55 and 90 years of age (inclusive), who are living in either an institutionalized setting or in a non-institutionalized setting where the subject is not living alone. In both the institutionalized and non-institutionalized settings, the subject must have a caregiver who can spend a minimum of 2 hours per day for 4 days per week with the subject in order to assess changes in the subject's condition. All subjects must have a diagnosis of probable Alzheimer's disease according to the National Institute of Neurological and Communicative Disorders and Stroke and the Alzheimer's Disease and Related Disorders Association (NINCDS-ADRDA) criteria.

The trial comprises a 2- to 42-day screening period, a 12-week double-blind treatment period, and a 30-day post-treatment follow-up period. In addition, for all subjects who terminate early from the trial, all attempts will be made to collect mortality data by telephone contact with the subject's caregiver at Week 16.

This trial will be monitored under the supervision of an independent Data Monitoring Committee (DMC). The DMC will monitor safety periodically, based on a predetermined

schedule. The details of the DMC structure and its roles and responsibilities will be documented in a DMC charter.

The trial is organized as follows:

Screening Period

The screening period will range from 2 days to 42 days and will begin when the informed consent form (ICF) is signed, prior to the initiation of any procedures. The screening period may be extended after discussion with and approval by the medical monitor. An interactive voice response system (IVRS) or interactive web response system (IWRS) will be used to obtain the subject study identification number for each subject with a signed ICF.

12-week, Double-blind Treatment Period

Based on a randomization scheme, eligible **CCI** subjects will be allocated in a 1:1:1 ratio at randomization to 1 of the following 3 treatment groups:

- Brexpiprazole 1 mg/day
- Brexpiprazole 2 mg/day
- Placebo

CCI

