Subjects will follow a titration schedule, depending upon their assigned treatment group, to gradually increase their dose to their assigned target dose.

Subjects unable to tolerate their assigned dose of brexpiprazole (or matching placebo) will be withdrawn from the trial. Down-titration is not allowed at any time during the study. If a subject is withdrawn, every effort will be made to complete all of the Week 12/Early Termination (ET) evaluations prior to administering any additional medications for the treatment of agitation or other prohibited medications.

Subjects will be evaluated at Baseline, Day 3, and Weeks 2, 4, 6, 8, 10, and 12 during the double-blind treatment period.

All attempts should be made to maintain the subjects' normal routine with regard to physician appointments. Individual circumstances that fall outside this general convention should be discussed with the medical monitor in order to determine appropriateness to

proceed. In addition, the subject's identified caregiver will be contacted by telephone at Weeks 3, 5, and 7 to assess compliance with IMP, confirm any changes to concomitant medications, and assure the subject's well-being. Trial-related efficacy and safety assessments will be performed as outlined in the study protocol.

Follow-up Period

All subjects, whether they complete the trial or are withdrawn prematurely for any reason, will be followed up for a safety evaluation 30 (+ 2) days after the last dose of the IMP during a clinic visit at either the investigator's site or residential facility, if applicable. If a clinic visit is not possible, the subject should be assessed by telephone contact with the subject and a caregiver. For all subjects who terminate early from the trial, all attempts will be made to collect mortality data by telephone contact with the subject's caregiver at Week 16.

Subjects who complete both the 12-week double-blind treatment period and the 30-day safety follow-up visit are eligible to enroll into Trial 331-13-211, which is a 2-month, observational, rollover trial to evaluate the safety of subjects with agitation associated with Alzheimer's disease who previously participated in Trial 331-12-283. For those subjects who plan to enroll into Trial 331-13-211, the 30-day safety follow-up visit for Trial 331-12-283 will occur as a clinic visit at either the investigator's site or residential facility, if applicable.

4 Sample Size and Power Justification

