9.1 Adverse Events

All adverse events will be coded by primary system organ class (SOC) and Medical Dictionary for Regulatory Activities (MedDRA version 19.0) preferred term (PT). AEs that are gender-specific, e.g., ovarian cancer, will have their incidence rates evaluated for the specific gender. The incidence of the following events will be summarized by treatment group:

- a) Treatment-emergent AEs (TEAE) by SOC and PT
- b) TEAEs at least 5% in the brexpiprazole group and twice greater than placebo
- c) TEAEs at least 2% in the brexpiprazole group and greater than placebo
- d) TEAEs by severity
- e) Potentially drug-related TEAEs
- f) TEAEs with an outcome of death
- g) Serious TEAEs
- h) TEAEs leading to discontinuations
- i) EPS-related AEs
- j) EPS-related AEs by time

- k) AEs of special interest
- l) TEAEs by gender, race, age and region

EPS-related AEs will be grouped into five categories.

- 1) Dystonic Events, which include cervical spasm, dystonia, emprosthotonus, muscle contractions involuntary, muscle rigidity, muscle spasms, muscle spasticity, myotonia, nuchal rigidity, oculogyration, opisthotonus, pleurothotonus, risus sardonicus, torticollis, and trismus;
- 2) Parkinsonian Events, which include akinesia, asterixis, athetosis, bradykinesia, cogwheel rigidity, essential tremor, extrapyramidal disorder, freezing phenomenon, gait festinating, hypertonia, hypokinesia, hypokinesia neonatal, intention tremor, masked facies, parkinson's disease, parkinsonian crisis, parkinsonian gait, parkinsonian rest tremor, parkinsonism, tremor, and tremor neonatal;
- 3) Akathisia Events, which include akathisia, hyperkinesia, and psychomotor hyperactivity;
- 4) Dyskinetic Events, which include ballismus, buccoglossal syndrome, choreoathetosis, clumsiness, dyskinesia, dyskinesia neonatal, dyskinesia oesophageal, fumbling, nodding of head, on and off phenomenon, and tardive dyskinesia;
- 5) Residual Events, which include chorea, huntington's chorea, muscle twitching, and myoclonus.

cci

The following AEs of special interest will be summarized by PT terms only:

- 1) Fall
- 2) Orthostatic hypotension
- 3) Syncope
- 4) Dizziness

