Treatment-emergent AEs are defined as AEs with an onset date on or after the start of double-blind treatment. In more detail, TEAEs are all adverse events which started after start of double blind study drug treatment; or if the event was continuous from baseline and was worsening, serious, study drug related, or resulted in death, discontinuation, interruption or reduction of study therapy. Adverse Events occurring up to 30 days after the last day of double-blind dosing will be included in the summary tables.

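### The readable SAP gives the Week 16 mortality data no summary, and its 30-day adverse event cut-off leaves early terminators with shorter coverage of fatal events than completers

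*SAP*

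**What the plan says.** Section 3 (Trial Design) sets out "a 12-week double-blind treatment period, and a 30-day post-treatment follow-up period". Under its Follow-up Period heading, all subjects, completers and withdrawals alike, "will be followed up for a safety evaluation 30 (+ 2) days after the last dose of the IMP". It then adds a second contact for one group, timed at Week 16: "For all subjects who terminate early from the trial, all attempts will be made to collect mortality data by telephone contact with the subject's caregiver". The opening of Section 3 makes the same commitment.

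Section 9.1 lists the adverse event summaries by treatment group as items a) to l), lettered without a break. The one item about death is f): "TEAEs with an outcome of death". The text that follows defines the start of the window: "Treatment-emergent AEs are defined as AEs with an onset date on or after the start of double-blind treatment". It then limits what enters the tables: "Adverse Events occurring up to 30 days after the last day of double-blind dosing will be included in the summary tables".

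The readable introduction to Section 9 does not name mortality or vital status among the standard safety variables. No readable sentence gives the Week 16 mortality data an analysis set, a time window or a table.

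**The concern.** The design appears to aim at knowing, for every subject, whether they were alive at about Week 16. Completers reach that point through the ordinary 30-day follow-up, and early terminators reach it through the extra call. The tabulation rule then counts from each subject's own last dose, which undoes this for early terminators. The earlier a subject stops, the less of the 16 weeks the death table covers.

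This matters because death is the most serious safety outcome in an elderly dementia population, and the counts will be small. Section 3 withdraws subjects who cannot tolerate their assigned dose and does not allow down-titration, so poor tolerability leads directly to a shorter window. If withdrawal differed between arms, coverage of fatal events would differ too. Without a stated rule, whether deaths learned of at Week 16 count would also be open to decision after unblinding.

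**Working it through.** The SAP states no mortality figure to reproduce, so the check is calendar arithmetic followed by a rough size.

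**Inputs from the SAP.** Treatment lasts 12 weeks, so a completer's last dose is on Day 84 (Section 3; target day in Section 10.1). The table cut-off is last dose + 30 days (Section 9.1). The mortality call is at Week 16 (Section 3), taken here as 16 × 7 = Day 112. Randomised subjects per arm: 132 (Section 4).

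**Coverage.** For last-dose day d, the window ends on Day d + 30. The gap to Week 16 is max(0, 112 − (d + 30)) = max(0, 82 − d).

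| Last dose (day) | Window ends (day) | Gap to Day 112 (days) |
|---|---|---|
| 14 | 44 | 68 |
| 28 | 58 | 54 |
| 42 | 72 | 40 |
| 56 | 86 | 26 |
| 70 | 100 | 12 |
| 82 | 112 | 0 |
| 84 (completer) | 114 | 0 |

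The gap falls only on subjects whose last dose is before Day 82. Its maximum is 81 days, for a last dose on Day 1.

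**Which deaths fall in the gap.** The rule limits when the adverse event occurs, not when the subject dies. Take a last dose on Day 14:
- An event that starts on Day 40 and is fatal on Day 70 is inside the window (40 ≤ 44) and is counted.
- An event that starts on Day 60 and is fatal on Day 70 is outside it (60 > 44) and is not counted, even if the Week 16 call reports the death.

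**Rough size (assumptions, not SAP figures).** Assume last-dose days of early terminators spread evenly over Days 1–83, 10–20% early termination, annual mortality of 5–40% at a constant hazard, and 132 subjects per arm followed to Day 112.
- Mean gap = (81 + 80 + … + 0)/83 = 3,321/83 = 40.0 days.
- Uncovered person-days per arm: 132 × 0.10 × 40.0 = 528; 132 × 0.20 × 40.0 = 1,056.
- Person-days per arm to Day 112: 132 × 112 = 14,784. Shares: 528/14,784 = 3.6%; 1,056/14,784 = 7.1%.
- Daily hazard = −ln(1 − annual mortality)/365.25, which is 0.000140 at 5% and 0.00140 at 40%.
- Expected deaths per arm in uncovered time: 528 × 0.000140 = 0.07; 1,056 × 0.00140 = 1.5.

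These are upper bounds for omitted deaths under the stated assumptions, because some deaths in the gap will come from events that began inside the window and are counted.

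**The case against.** The strongest reply is that a 30-day adverse event window matching the 30-day safety follow-up is ordinary practice, and that it does not contradict a separate collection of vital status. The Week 16 deaths may have a table of their own. Section 13 (Proposed List of Summary Tables), a block inside Section 9.1, part of the Section 9 introduction, and Sections 9.6 and 9.8 are redacted or not shown, and text missing for that reason is not missing from the plan. This stands as a limit: nobody can say from the readable text that the Week 16 data go unused. It does not remove the point. The list a) to l) is complete, the cut-off sentence is readable in full, and followed as written they give unequal coverage.

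Three stronger readings are tempting, and the document does not support them:
- A reader might infer that every death more than 30 days after last dose is dropped. The cut-off applies to the occurrence of the event, so a later death from an event inside the window still counts.
- A reader might infer a biased mortality comparison. Section 9.1 plans incidence by treatment group, with no mortality test or hypothesis. Bias between arms would need withdrawal or late mortality to differ by arm, and the SAP gives neither rate.
- A reader might suppose that the hazard rises several-fold after stopping and arrive at a much larger missed share. Nothing in the SAP supports such a multiplier.

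It is also fair to say that the expected number of affected deaths is small.

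**Conclusion.** The point holds in a limited form and deserves a change. As far as the SAP can be read, it assigns no summary to the Week 16 mortality data, and its 30-day rule leaves out fatal events that start later than that in early terminators, while completers are covered beyond Week 16. The gap is 82 minus the last-dose day, and this follows from the SAP's own timings once Week 16 is taken as Day 112. The size in deaths, roughly 0.07 to 1.5 per arm at most, rests wholly on assumed termination, timing and mortality rates. In a sparse table a single death can still change the impression. The conclusion is conditional on there being no Week 16 death table in the parts that are not visible. If there is one, Section 9.1 need only refer to it.

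**What to change.** Add a short paragraph to Section 9.1 specifying a summary of all-cause deaths through Week 16, by randomised arm in the Safety Sample, as number and percent. It should:
- apply whatever the adverse event window;
- draw on the 30-day follow-up and the Week 16 call;
- report the number of subjects with unknown vital status in each arm.

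Keep the existing 30-day table of fatal treatment-emergent events as the on-treatment view, and state there that inclusion depends on the onset of the event and not on the date of death. Risk differences against placebo with exact confidence intervals and a Kaplan-Meier display are optional.

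The cost is one paragraph and one table from data the trial already collects, with no new procedure. The drawback is that vital status at Week 16 will be unknown for some subjects, which is why the unknowns should be shown by arm.

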9.2 Clinical Laboratory Tests

9.2.1 Change from Baseline in Lab Tests

Summary statistics for mean and mean change from baseline in the routine clinical laboratory measurements, prolactin concentrations, coagulation parameters (PT, aPTT, and INR), HbA1c, cortisol, ACTH, and TSH will be provided by treatment and by visit.

9.2.2 Potentially Clinically Relevant Values

In addition, the incidence of treatment-emergent potentially clinically relevant (PCR) values identified using prospectively defined criteria in Appendix 1 for laboratory tests will be summarized by treatment group. A listing of PCRs by subject and by test will be provided.

9.2.3 Potentially Liver Injury Related Laboratory Test

Total bilirubin level will be checked for any subjects with increased ALT or AST levels greater or equal to three times the upper normal limits (or baseline).

Liver injury related laboratory test results will be summarized for subjects who met following criteria in the Short-term Controlled Trials and Long-term Open-label Trials groups. The corresponding listing will be provided as well.

- AST or ALT $\geq 3 \times$ ULN and
- T_Bili $\geq 2 \times$ ULN

9.2.4 Metabolic Change

In addition to mean change from baseline, the incidence of treatment emergent significant changes in fasting lipids, fasting glucose, and metabolic syndrome will be summarized by treatment group using the following criteria.

Criteria for Treatment-Emergent Significant Change in Lipids and Glucose		
LAB PARAMETER	BASELINE*	ANYTIME POST BASELINE
LDL Direct, Fasting (MG/DL)	Borderline 100-<160 Normal/Borderline <160 Normal <100 Any Value	High ≥ 160 High ≥ 160 Borderline/High ≥ 100 Increased ≥ 30
HDL Cholesterol, Fasting (MG/DL)	Normal ≥ 40 Any Value	Low <40 Decreased ≥ 20
Triglycerides, Fasting (MG/DL)	Normal <150 Borderline 150-<200 Normal/Borderline <200 Normal <150	High 200-<500 High 200-<500 High 200-<500 Borderline/High/Very High ≥ 150

Criteria for Treatment-Emergent Significant Change in Lipids and Glucose		
LAB PARAMETER	BASELINE*	ANYTIME POST BASELINE
	Any Value	Increased ≥ 50
Glucose Fasting, Serum (MG/DL)	Normal <100 Impaired 100-<126 Normal/Impaired <126 Any Value	High ≥ 126 High ≥ 126 High ≥ 126 Increased ≥ 10

* Baseline is calculated from day 0; if day 0 is unavailable screen visit will be used

Criteria for Treatment-Emergent Metabolic Syndrome	
DESCRIPTION	ANYTIME POST BASELINE*
Central Obesity	Waist Circumference $\geq 102\text{cm(MALE)}, \geq 88\text{cm (FEMALE)}$
Dyslipidemia	Triglycerides $\geq 150\text{mg/dl}$
Dyslipidemia	HDL $< 40\text{mg/dl (MALE)}, < 50\text{mg/dl (FEMALE)}$
Supine Blood Pressure	Systolic $\geq 130\text{mmHg}$ and Diastolic $\geq 85\text{mmHg}$
Glucose Fasting, Serum	$\geq 100\text{mg/dl}$
Metabolic Syndrome	Met 3 Or More of the Above Criteria at a Visit

* Baseline is calculated from day 0; if day 0 is unavailable screen visit will be used

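### The metabolic-syndrome summary is labelled treatment-emergent but its case rule has no baseline condition, so pre-existing cases are counted as new

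*SAP*

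**What the plan says.** Section 9.2.4 of the SAP states that "the incidence of treatment emergent significant changes in fasting lipids, fasting glucose, and metabolic syndrome will be summarized by treatment group". Two criteria tables follow.

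- The lipid and glucose table is headed "LAB PARAMETER BASELINE* ANYTIME POST BASELINE". Its rows pair a baseline category with a post-baseline category or, where any baseline value is allowed, require a change of a stated size.
- The second table is titled "Criteria for Treatment-Emergent Metabolic Syndrome". Beside the description it has one column, "ANYTIME POST BASELINE". It lists five components (waist, triglycerides, HDL, blood pressure, fasting glucose), and the syndrome itself is defined by "Met 3 Or More of the Above Criteria at a Visit".

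A footnote to the second table reads "Baseline is calculated from day 0; if day 0 is unavailable screen visit will be used". It says which visit supplies baseline, but not what is done with the value.

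The row "Supine Blood Pressure" joins systolic of at least 130 mmHg and diastolic of at least 85 mmHg with the word and, so both limits must be met.

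**The concern.** An incidence of treatment-emergent cases should count subjects who acquire the condition on treatment. The rule as written counts everyone who has it at any post-baseline visit, including those who entered the trial with it. Such subjects should be about equally frequent in all randomized arms, so they add a similar amount to each rate. The reported figure is then closer to a period prevalence than an incidence, and a real difference in new onset looks proportionally smaller. Evaluating safety and tolerability against placebo is the trial's secondary objective (SAP Section 2), so a table under this label should measure what the label says.

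A smaller question concerns the blood-pressure component: with both limits required, isolated systolic or isolated diastolic elevation does not count.

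**Working it through.** The SAP states no rate, count or power for metabolic syndrome, so there is no planned figure to reproduce. The check has three parts.

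**1. The rule applied to test subjects (all men).**

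- Waist 106 cm, triglycerides 170 mg/dL, HDL 38 mg/dL, glucose 110 mg/dL, blood pressure 128/76, identical before and during treatment. Four components are met at both times. The rule counts him as treatment-emergent, although nothing has changed.
- Waist 106 cm, triglycerides 170 mg/dL, HDL 45 mg/dL, glucose 95 mg/dL, blood pressure 165/78. Waist and triglycerides are met; blood pressure is not, because diastolic is below 85. Two components, not counted.
- The same man with blood pressure 125/92. Systolic is below 130; two components, not counted. At 130/85 he would have three and would be counted.

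**2. How the rest of the SAP handles baseline.** The QT/QTc table in Section 9.4 defines new onset as reaching the cut-off on treatment without having reached it at baseline. Appendix 2 has a change-from-baseline column, and for orthostatic hypotension, where baseline is ignored, it says so. Section 9.1 defines treatment-emergent for adverse events only. No general definition fills the gap in Section 9.2.4.

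**3. Size of the dilution.** Let p be baseline prevalence, r the proportion of prevalent subjects who meet the rule again at any post-baseline visit, and q new onset among subjects free at baseline. All three are assumptions.

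Rate as written = p × r + (1 − p) × q

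With r = 1 and q = 5% (placebo) and 12% (drug), the true ratio is 12/5 = 2.4:

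| p | Placebo | Drug | Ratio |
|---|---|---|---|
| 20% | 0.20 + 0.80 × 0.05 = 24.0% | 0.20 + 0.80 × 0.12 = 29.6% | 1.23 |
| 30% | 0.30 + 0.70 × 0.05 = 33.5% | 0.30 + 0.70 × 0.12 = 38.4% | 1.15 |
| 40% | 0.40 + 0.60 × 0.05 = 43.0% | 0.40 + 0.60 × 0.12 = 47.2% | 1.10 |

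Full persistence is not essential. At p = 30% and r = 0.80 the rates are 0.24 + 0.035 = 27.5% and 0.24 + 0.084 = 32.4%, a ratio of 1.18.

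A second set, with q of 5% and 10% (true ratio 2.0), p of 20% to 50% and r of 0.80 to 0.95, gives ratios from 1.20 down to 1.05. At the 132 subjects per arm in SAP Section 4, about 26 to 66 placebo subjects would be flagged, of whom about 21 to 63 (80% to 95%) already had the syndrome at baseline.

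The denominator matters too. Excluding prevalent cases from the numerator only, at p = 30%, gives 0.70 × 0.05 = 3.5% and 0.70 × 0.12 = 8.4%. The ratio of 2.4 is restored, but the rates understate the 5% and 12% among subjects at risk.

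**The case against.** The strongest reply is that the exclusion is plainly intended. The lead-in speaks of treatment-emergent changes, the table title repeats the label, and a footnote on baseline has a purpose only if baseline is used. That stands as evidence of intent, and a careful programmer might add the condition unprompted. It does not repair the rule. The criteria as printed give a different count, the SAP states such conditions elsewhere, and the denominator would still be open, so two programmers could produce different tables.

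It is also fair that the consequence is limited. Section 9.2.4 plans no test of this summary. Other analyses would show metabolic change: the shifts in individual lipids and glucose, mean laboratory changes (Section 9.2.1), waist circumference (Section 9.3), and weight by ANCOVA with the 7% gain and loss categories (Section 9.5). A reader might infer that a true metabolic signal would be lost from the report; the plan does not support that. Only the composite count is exposed.

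A reader might also infer that the joint blood-pressure requirement is a drafting error and that either limit should suffice. The SAP cites no source definition of the syndrome. Appendix 2 lists systolic and diastolic separately, but for another purpose and with other limits. The document shows what the joint rule does, not that it is wrong. Nor can the component be called nearly inactive. Assuming systolic mean 130 and SD 16, diastolic SD 10 and correlation 0.5 to 0.7, it flags 11% to 13% of single readings at a mean diastolic of 74 and 27% to 31% at 82. None of these inputs is in the SAP.

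**Conclusion.** The baseline gap is a real defect in the stated rule. Followed literally, Section 9.2.4 counts unchanged pre-existing cases as treatment-emergent, inflates the incidence in every arm and moves the ratio between arms toward 1. The direction holds whenever some subjects have the syndrome at baseline and keep it, and new onset differs between arms. The size depends on assumed prevalence, persistence and new onset: a true ratio of 2.4 falls to about 1.23 to 1.10 at 20% to 40% prevalence with full persistence.

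The blood-pressure row is a question for the sponsor, not an established error. The whole point concerns one descriptive safety summary; the primary and key secondary analyses and their error control are untouched.

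**What to change.** In Section 9.2.4, define treatment-emergent metabolic syndrome as fewer than three criteria at baseline and three or more at any one post-baseline visit. Use subjects not meeting the syndrome at baseline as the denominator, and show baseline prevalence by arm beside the incidence. The existing footnote then has a rule to serve.

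Ask the sponsor to confirm that requiring both blood-pressure limits is intended, and to state the source or reason. Settle this first, because the component also determines who meets the syndrome at baseline and so who is in the denominator.

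The cost is a few lines of text and a changed denominator. The downside is a smaller one: at 132 per arm and an assumed prevalence of 20% to 40%, about 106 down to 79 subjects per arm (132 × 0.80 and 132 × 0.60).
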